3.2. Blinding

The blinding of the study is double blind to the investigator and patients. The placebo treatment was performed with the same therapy head, which was also fitted with a placebo stand-off. This stand-off contained shock wave-absorbing material, a layer of air, and air-filled microspheres.

Performance of the placebo stand-off was validated by measuring the output pressure in a laboratory setup. The setting was identical to the verum treatment. The blinding included the specification that neither the patient nor the investigator/follow-up observer was aware of placebo or verum assignment.

4. SUBJECTS

4.1. Number and Source

Approximately 60 patients will be enrolled and a total of 48 evaluable patients will be completed within the three-year study period.

4.2. Inclusion Criteria

Patients must meet all the following criteria to be eligible to enter the trial:

- 4.2.1. Adult male or female, at least 20 years of age.
- 4.2.2. History of UAB (defined as bothersome chronic incomplete bladder emptying) for at least 3 months documented in the medical record with recurring UAB symptoms.
- 4.2.3. No UAB symptom relief (unresponsiveness) with previous used medications and/or other treatments.
- 4.2.4. Voiding difficulty (complains of difficulty emptying the bladder).
- 4.2.5. UAB consistent with diabetes, MS, Parkinson's disease, or aging idiopathic.
- 4.2.6. Post void residual ≥ 100 mL.
- 4.2.7. Bladder capacity > 200 mL and < 800 mL.
- 4.2.8. Pressure flow Urodynamic testing demonstrating impaired detrusor contractility or areflexia without evidence of BOO, with maximum detrusor pressure Pdet at Qmax (Pdet@Qmax) of < 20 cmH₂O and Maximum flow rate (Qmax) < 15 mL/sec for female and BCI <100 and BOOI < 40 for male [2, 3].
- 4.2.9. Total UAB Questionnaire Score ≥ 3 .
- 4.2.10. Females of child-bearing potential agree to use reliable birth control for the entire study duration.
- 4.2.11. Willing and capable of understanding and complying with all requirements of the protocol, including proper completion of the voiding diaries and self-administered questionnaires.
- 4.2.12. Free of active urinary tract infection.
- 4.2.13. Free of bladder outlet obstruction on enrollment.
- 4.2.14. Patient or his/her legally acceptable representative has signed the written informed consent form.
- 4.2.15. Subject on clean intermittent catheterization (CIC) should have been on CIC for at least 1 month and should be able to void spontaneously and not be completely dependent on CIC.

4.3.Exclusion Criteria

- 4.3.1. Female patients who is pregnant, lactating, plans to become pregnant, or with child-bearing potential without contraception.
- 4.3.2. Simultaneously participating in another investigational drug or device study or use of any investigational drug(s) or therapeutic device(s) within 3 months preceding enrollment.
- 4.3.3. Has been treated with an investigational device, drug, or procedure for UAB within the last 3 months.
- 4.3.4. History of cancer in pelvic organs, ureters, or kidneys or any cancer that has undergone treatment within the past 12 months.
- 4.3.5. Medical condition or disorder that may limit life expectancy or that may cause protocol deviations (e.g. unable to perform self-evaluations/accurately report medical history, and/or urinary symptoms).
- 4.3.6. History of spinal cord injury affecting urinary function.
- 4.3.7. Patients with uncontrolled acute urinary tract infection. An active urinary tract infection as evidenced by positive urine culture at the time of baseline assessment.
If a UTI is confirmed in the baseline sample (e.g., positive urine culture containing > 100,000 cfu/mL in midstream urine), the run-in period should be stopped. After successful treatment of the UTI, the patient can be rescreened and if eligible enroll in the study. If the patient has asymptomatic bacteriuria (i.e., a positive urine culture without clinical signs and symptoms of a UTI), the patient should not be excluded [3].
- 4.3.8. Currently taking medication(s) that may affect urination, including prescription drugs (i.e. anticholinergics, tricyclic antidepressants, bethanechol), over the counter drugs, dietary and/or herbal supplements. Alpha adrenergic blockers are allowed to use in a stable condition (longer than 1 month and keeping use during the study period).
- 4.3.9. Pelvic organ prolapses beyond the introitus (e.g., cystocele, rectocele).

- 4.3.10. Prior mesh surgery for stress urinary incontinence or pelvic prolapse.
- 4.3.11. Any other condition which per investigators' judgement, may affect the patient's safety (e.g. significant cardiovascular disease, asthma or other breathing disorders).
- 4.3.12. Patients with bladder outlet obstruction on enrollment.
- 4.3.13. Patients with any contraindication to be urethral catheterization during diagnostic test or treatment or follow-up period.
- 4.3.14. Patients have laboratory abnormalities at screening including:
ALT > 3 x upper limit of normal range
AST > 3 x upper limit of normal range
Serum creatinine level > 2 x upper limit of normal range.
- 4.3.15. Patients with any other serious disease considered by the investigator not in the condition to enter the trial.
- 4.3.16. Patients with cortisone treatment 6 week before first LESW therapy

Other single item of Lab examination also can be retested per Investigator's discretion if abnormality. Patient will be rescreened and randomized into the study once confirmed eligible.

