5. STUDY PROCEDURE

5.1. General Study Design

This study is designed as a double-blind, randomized, paralleled, controlled trial. The DU/UAB confirmed patients will be randomly assigned to receive (1) ESWT or (2) placebo control group. The treatments will be evaluated at baseline screening and at least 2 study required visits (treatment visit and primary end-point evaluation visit) will be performed for PVR, symptom score recording, urodynamic studies, adverse event recording and global satisfaction assessments. Urine samples (30 ml) will also be collected at each visit for analysis of the urinary NGF and cytokines levels.

Procedures of LESW

Studied patients are requested to void completely before treatment. Urine samples (30 ml) will be collected for analysis of the urinary NGF and cytokines levels. The patients are placed in supine position in an examination room at out-patient clinic.

The shock wave applicator, FS-I (“LITEMED” LM-ESWT-mini system, Taiwan), will be gently placed on the skin area over the bladder dome, right upper lateral wall, right lower lateral wall, left upper lateral wall, and left lower lateral wall during once a week for 6 weeks, with 2500 shocks, frequency of 4 pulses per second, and maximum total energy flow density 0.25 mJ/mm². The current shock wave intensity and number used was followed from reference [1].

Patients will be asked about any painful sensation that they experience during the treatment. Vital signs (body temperature, blood pressure, heart rate and respiration rate) will be recorded at pre-treatment, and 30 mins following treatment. During the treatment, patient will be stayed in a treatment room and accompanied by a research assistant.

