5.2. Study Visits and Evaluations

5.2.1. Screening Visit (V0, 2 weeks before the treatment day)

- 5.2.1.1. Explain the nature of the study and have patients to read and sign an Informed Consent Form.
- 5.2.1.2. Screen patients for inclusion/exclusion criteria (section 4.2 and 4.3).
- 5.2.1.3. Medical History of DU/UAB and previous treatment modalities.
- 5.2.1.4. Vital signs monitoring and general physical examinations of all systems, EKG examination to rule out abnormal cardiac diseases, and biochemistry examinations including CBC, PT, APTT, ALT, AST and Cr.
- 5.2.1.5. Check Uroflowmetry and record, urodynamic study and PVR volume.
- 5.2.1.6. Urinalysis for WBC, RBC, pH, Protein, Glucose and Bacteria if patient has symptoms suggestive of urinary tract infection.

5.2.1.7. Physical assessments to exclude bladder outlet obstruction or bladder pathology.

5.2.1.8. Record concomitant medication.

5.2.1.9. Dispense three-day voiding diary to record for 3 days before the treatment day.

5.2.1.10. Record UAB symptom score.

5.2.1.11. Discontinue all previous UAB-related medication.

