5.2.2. Randomization and Treatment Visit (V1, Week 0)

5.2.2.1 A randomization number is given to eligible patient.

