5.2.2.2 Inform patient of the possible adverse events

5.2.2.3 Review three-day voiding diary.

5.2.2.4 Collect 30 ml urine for analysis of the urinary NGF and cytokines levels.

5.2.2.5 ESWT given.

5.2.3. Treatment Visit (V2, Week 1, 1 week \pm 3 days after the V1 treatment day)

5.2.3.1 Vital signs monitoring, and confirm eligibility of patients.

5.2.3.2 ESWT given.

5.2.4. Treatment Visit (V3, Week 2, 1 week \pm 3 days after the V2 treatment day)

5.2.4.1 Vital signs monitoring, and confirm eligibility of patients.

5.2.4.2 ESWT given.

5.2.5. Treatment Visit (V4, Week 3, 1 week \pm 3 days after the V3 treatment day)

5.2.5.1 Vital signs monitoring, and confirm eligibility of patients.

5.2.5.2 ESWT given.

5.2.6. Treatment Visit (V5, Week 4, 1 week \pm 3 days after the V4 treatment day)

5.2.6.1 Vital signs monitoring, and confirm eligibility of patients.

5.2.6.2 ESWT given.

5.2.7. Treatment Visit (V6, Week 5, 1 week \pm 3 days after the V5 treatment day)

5.2.7.1 Vital signs monitoring, and confirm eligibility of patients.

5.2.7.2 ESWT given.

5.2.7.3 Dispense three-day voiding diary to record for 3 days before the next visit day.

5.2.8 Evaluation Visit I (Primary end-point, V7, 4 weeks \pm 3 days after the V6 treatment day)

5.2.8.1 Review patients voiding diary for urinary frequency, functional bladder capacity, and record reported UAB symptom score, and GRA.

5.2.8.2 Vital signs monitoring and record adverse events.

5.2.8.3 Check urinalysis for urinary tract infection if patient has symptoms.

5.2.8.4 Check uroflowmetry for maximum flow rate, voided volume, and PVR volume.

5.2.8.5 Appointment for the next visit at 12 weeks \pm 3 days after the V6.

5.2.8.6 Dispense three-day voiding diary to record for 3 days before the next visit day.

5.2.8.7 Collect 30 ml urine for analysis of the urinary NGF and cytokines levels.

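### Pregnant women are excluded, but no visit from V0 to V8 names a pregnancy test before suprapubic shock wave treatment or its repeat course

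*Protocol*

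**What the plan says.** **Eligibility.** Protocol 4.3.1 excludes "Female patients who is pregnant, lactating, plans to become pregnant, or with child-bearing potential without contraception". Section 4.2.1 admits women from age 20 with no upper limit, and 4.2.10 states: "Females of child-bearing potential agree to use reliable birth control for the entire study duration".

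**Screening (V0).** Step 5.2.1.2 has each patient checked against sections 4.2 and 4.3. The laboratory work in 5.2.1.4 is described as "biochemistry examinations including CBC, PT, APTT, ALT, AST and Cr". Urinalysis (5.2.1.6) is done only when symptoms suggest infection.

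**Randomisation and first treatment (V1).** The first step, 5.2.2.1, reads "A randomization number is given to eligible patient". Urine comes three steps later, at 5.2.2.4: "Collect 30 ml urine for analysis of the urinary NGF and cytokines levels". ESWT follows.

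**Later treatment visits (V2–V6).** Each lists "Vital signs monitoring, and confirm eligibility of patients" and then ESWT. No urine collection is listed at these visits, although section 5.1 says "Urine samples (30 ml) will also be collected at each visit for analysis of the urinary NGF and cytokines levels".

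**Repeat course.** Section 2, under the 3-month follow-up, provides further ESWT for patients in whom treatment has not worked by then. It describes no procedures for that course.

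**The concern.** Most parts of 4.3.1 can be settled by asking: lactation, plans for pregnancy and use of contraception. Current pregnancy cannot always be settled that way. Agreement to use birth control during the study does not rule out a conception before consent, nor a contraceptive failure.

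The treatment is focused shock waves over the suprapubic region with a focus depth of 30–90 mm, given in six weekly sessions. At stake is participant safety: a woman whom 4.3.1 is meant to keep out could be treated because nothing in the visit schedule would reveal her pregnancy. There is also a smaller trial-conduct cost. A pregnancy found after the randomisation number has been issued concerns a patient already in the trial, whereas one found beforehand is a screen failure.

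**Working it through.** **Figures in the plan.** The plan gives no figure for pregnancy testing. The only plan figure used here is the enrolment of 60, which reproduces: 48 / (1 − 0.20) = 60 (SAP 7.4). The power statement also reproduces. With 24 per group, difference 50 and SD 60, the noncentrality is 50 / (60 × √(2/24)) = 2.887 on 46 degrees of freedom, giving 80.677%. Nothing below changes either figure.

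**1. Count over the visit schedule (section 5.2).** Visits V0 to V8 are nine visits. Visits naming a serum or urine pregnancy test: 0 of 9.

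**2. Comparison with other criteria that need an objective measurement.**
- ALT, AST and creatinine limits (4.3.14): measured at 5.2.1.4.
- Residual volume and urodynamic limits (4.2.6, 4.2.8): measured at 5.2.1.5.
- Outlet obstruction (4.3.12): assessed at 5.2.1.7.
- Questionnaire score (4.2.9): recorded at 5.2.1.10.
- Current pregnancy (4.3.1): no method named.

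**3. Exposure if an unrecognised pregnancy enters the ESWT arm at V1.** Inputs from sections 1 and 3: 2500 shocks at 4 per second, six weekly sessions. Assumption: 2500 is the total for a session.
- One session: 2500 / 4 = 625 s = 10.4 min.
- Recognised after one session: 1 × 2500 = 2,500 shocks.
- Not recognised during the course: 6 × 2500 = 15,000 shocks.
- Time from V1 to V6: 5 × 7 = 35 days. With ±3 days at each interval: 5 × 4 = 20 to 5 × 10 = 50 days.

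**4. Would a test at V1 cover the repeat course?** The repeat course cannot start before V8, nominally 12 weeks after V6.
- Nominal: 35 + 84 = 119 days after V1.
- With the ±7 days of section 5.2.9: 20 + 77 = 97 to 50 + 91 = 141 days.
- With the ±3 days of step 5.2.8.5, which differs: 20 + 81 = 101 to 50 + 87 = 137 days.

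Under either window a V1 result is more than three months old, so it does not cover the repeat course.

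**5. Why V1 rather than V0.** V0 lies two weeks before treatment. A test there leaves 14 days uncovered, while a test at V1 leaves none before the first session.

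**6. Number of women.** The documents give none. Assuming 0–10% of 60: 0 to 6 women, of whom about 0 to 3 would be expected in the ESWT arm under 1:1 allocation. Scheduled tests: 0–6 at V1 plus at most 0–6 before a repeat course = 0–12.

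**The case against.** The best defence is that the protocol does apply the criterion. Step 5.2.1.2 covers 4.3.1, only an eligible patient is randomised, and eligibility is confirmed again at V2–V6. The investigator carries the duty and chooses the method, as for mesh surgery, cancer history or prolapse. The laboratory list is open-ended, so a site may test for pregnancy as routine. All of this stands. A reader might infer that the exclusion is never applied; the documents do not support that. What remains is narrower: surgery and cancer history can be established by asking or from the record, and prolapse by examination, but an unrecognised pregnancy needs a test, and the protocol requires none.

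The population may also be very small. Women without contraception or planning pregnancy are already excluded, leaving only pregnancies unrecognised despite that. This stands and limits the weight of the point, but 4.2.10 expressly provides for women of child-bearing potential.

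The repeat course lacks described procedures of every kind, so the missing pregnancy check there is one part of a wider gap, and contraception is required throughout the study. That is fair. The check still needs stating, because the V1 test would be out of date.

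A reader might extend the argument to urinary infection, since no visit lists a urine culture. That does not hold as a comparable gap. Section 4.3.7 itself names the culture, its baseline timing and an example threshold, and it does not exclude asymptomatic bacteriuria. The visit list merely does not repeat it.

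**Conclusion.** The point holds as a gap in a named method: 4.3.1 is screened for, but no visit requires the test that would detect an unrecognised pregnancy before suprapubic shock waves. The absence (0 of 9 visits) is certain from the text. The exposure range of 2,500 to 15,000 shocks rests on reading 2500 as the session total. It applies only if such a pregnancy occurs in the ESWT arm, and it is neither a probability nor an estimate of harm. The 0–6 women rest on an assumed share of 0–10%; the true number may be zero.

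A reader might infer that the efficacy result is at risk. Nothing in the documents supports that: the primary PVR conclusion, sample size and power are untouched. This is a change the sponsor should make because it protects participants at almost no cost.

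**What to change.** 1. **V1.** Move the urine collection (5.2.2.4) ahead of the randomisation number (5.2.2.1). Do a urine pregnancy test in women of child-bearing potential and randomise only if it is negative.
2. **V2–V6.** Within the existing eligibility step, ask about a missed period and, if the answer is yes, test before ESWT. Section 5.1 implies that urine is available at every visit, but the V2–V6 lists do not include it, so a spot sample may be needed.
3. **Repeat course.** Repeat the test before its first session.
4. **Positive result after randomisation.** Stop treatment, but keep the patient in follow-up and in the ITT set. This fits SAP 7.1, which counts patients who were screened and treated. It also matters under SAP 7.3, where an incomplete observation is simply left missing.

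**Cost.** 0–12 scheduled urine tests under the 0–10% assumption, a few more prompted by a missed period, and possibly a few screen failures. The V1 test needs no additional sample, because urine is already collected at that visit.

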5. STUDY PROCEDURE

5.1. General Study Design

This study is designed as a double-blind, randomized, paralleled, controlled trial. The DU/UAB confirmed patients will be randomly assigned to receive (1) ESWT or (2) placebo control group. The treatments will be evaluated at baseline screening and at least 2 study required visits (treatment visit and primary end-point evaluation visit) will be performed for PVR, symptom score recording, urodynamic studies, adverse event recording and global satisfaction assessments. Urine samples (30 ml) will also be collected at each visit for analysis of the urinary NGF and cytokines levels.

Procedures of LESW

Studied patients are requested to void completely before treatment. Urine samples (30 ml) will be collected for analysis of the urinary NGF and cytokines levels. The patients are placed in supine position in an examination room at out-patient clinic.

The shock wave applicator, FS-I (“LITEMED” LM-ESWT-mini system, Taiwan), will be gently placed on the skin area over the bladder dome, right upper lateral wall, right lower lateral wall, left upper lateral wall, and left lower lateral wall during once a week for 6 weeks, with 2500 shocks, frequency of 4 pulses per second, and maximum total energy flow density 0.25 mJ/mm². The current shock wave intensity and number used was followed from reference [1].

Patients will be asked about any painful sensation that they experience during the treatment. Vital signs (body temperature, blood pressure, heart rate and respiration rate) will be recorded at pre-treatment, and 30 mins following treatment. During the treatment, patient will be stayed in a treatment room and accompanied by a research assistant.

5.2. Study Visits and Evaluations

5.2.1. Screening Visit (V0, 2 weeks before the treatment day)

- 5.2.1.1. Explain the nature of the study and have patients to read and sign an Informed Consent Form.
- 5.2.1.2. Screen patients for inclusion/exclusion criteria (section 4.2 and 4.3).
- 5.2.1.3. Medical History of DU/UAB and previous treatment modalities.
- 5.2.1.4. Vital signs monitoring and general physical examinations of all systems, EKG examination to rule out abnormal cardiac diseases, and biochemistry examinations including CBC, PT, APTT, ALT, AST and Cr.
- 5.2.1.5. Check Uroflowmetry and record, urodynamic study and PVR volume.
- 5.2.1.6. Urinalysis for WBC, RBC, pH, Protein, Glucose and Bacteria if patient has symptoms suggestive of urinary tract infection.

5.2.1.7. Physical assessments to exclude bladder outlet obstruction or bladder pathology.

5.2.1.8. Record concomitant medication.

5.2.1.9. Dispense three-day voiding diary to record for 3 days before the treatment day.

5.2.1.10. Record UAB symptom score.

5.2.1.11. Discontinue all previous UAB-related medication.

5.2.2. Randomization and Treatment Visit (V1, Week 0)

5.2.2.1 A randomization number is given to eligible patient.

5.2.2.2 Inform patient of the possible adverse events

5.2.2.3 Review three-day voiding diary.

5.2.2.4 Collect 30 ml urine for analysis of the urinary NGF and cytokines levels.

5.2.2.5 ESWT given.

5.2.3. Treatment Visit (V2, Week 1, 1 week \pm 3 days after the V1 treatment day)

5.2.3.1 Vital signs monitoring, and confirm eligibility of patients.

5.2.3.2 ESWT given.

5.2.4. Treatment Visit (V3, Week 2, 1 week \pm 3 days after the V2 treatment day)

5.2.4.1 Vital signs monitoring, and confirm eligibility of patients.

5.2.4.2 ESWT given.

5.2.5. Treatment Visit (V4, Week 3, 1 week \pm 3 days after the V3 treatment day)

5.2.5.1 Vital signs monitoring, and confirm eligibility of patients.

5.2.5.2 ESWT given.

5.2.6. Treatment Visit (V5, Week 4, 1 week \pm 3 days after the V4 treatment day)

5.2.6.1 Vital signs monitoring, and confirm eligibility of patients.

5.2.6.2 ESWT given.

5.2.7. Treatment Visit (V6, Week 5, 1 week \pm 3 days after the V5 treatment day)

5.2.7.1 Vital signs monitoring, and confirm eligibility of patients.

5.2.7.2 ESWT given.

5.2.7.3 Dispense three-day voiding diary to record for 3 days before the next visit day.

5.2.8 Evaluation Visit I (Primary end-point, V7, 4 weeks \pm 3 days after the V6 treatment day)

5.2.8.1 Review patients voiding diary for urinary frequency, functional bladder capacity, and record reported UAB symptom score, and GRA.

5.2.8.2 Vital signs monitoring and record adverse events.

5.2.8.3 Check urinalysis for urinary tract infection if patient has symptoms.

5.2.8.4 Check uroflowmetry for maximum flow rate, voided volume, and PVR volume.

5.2.8.5 Appointment for the next visit at 12 weeks \pm 3 days after the V6.

5.2.8.6 Dispense three-day voiding diary to record for 3 days before the next visit day.

5.2.8.7 Collect 30 ml urine for analysis of the urinary NGF and cytokines levels.

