2. OBJECTIVE AND ENDPOINTS

The objective of this study is to evaluate the efficacy and safety of ESWT for the treatment of DU/UAB.

The primary and secondary endpoints are described as shown below:

(1) Primary End-point (1 month)

The efficacy of LESW will be evaluated for:

Net changes of the mean post void residual (PVR) volume (mL) from baseline to 1 month after the treatment day.

(2) Secondary end-points

Efficacy

The efficacy of ESWT will be evaluated for:

- (1) Net changes of the following parameters from baseline to 1 month after the treatment day: functional bladder capacity (FBC), voiding frequency at daytime and voiding frequency at night time, incontinence, as record in 3-day voiding diary.
- (2) Global response assessment (GRA) of satisfaction by the patient (categorized into -3, -2, -1, 0, 1, 2, 3, indicating markedly worse to markedly improved) at 1 month after the last treatment day. An improvement of GRA by 2 scales at 1 months is considered effective.
- (3) Net changes of the maximum flow rate, voided volume, Pdet@Qmax, and postvoid residual volume from baseline to 1 month after the treatment day.

(4) Changes of Underactive Bladder Questionnaire (UAB-Q) score.

(5) Changes of urinary nerve growth factor and cytokines level from baseline to 1 month after treatment day.

Safety

(1) Local adverse event incidences (hematuria, miction pain, UTI, urinary retention). The severity of adverse event is categorized as indicated below:

Severity of AE	Description
Mild	Transient and easily tolerable, not affecting usual daily activities
Moderate	Causes patient's discomfort, interrupting usual daily activities
Severe	Causes considerable interference with daily activities and may be incapacitating or life-threatening

(2) Systemic Adverse Events:

Any systemic adverse event occurring after ESWT will be asked to report and patients will be properly investigated and treated. The cause for systemic adverse event may be not related with ESWT.

(3) Changes in physical examinations.

(4) Changes in blood pressure and other laboratory test results will be examined if patients have severe adverse events or physical examinations reveal abnormalities.

(3) Follow-up (3 months)

Efficacy

The efficacy of ESWT will be evaluated for:

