5.2.9 Evaluation Visit II (V8, 12 week \pm 7 days after the V6)

5.2.9.1 Review patients voiding diary for urinary frequency, functional bladder capacity, and record reported UAB symptom score, and GRA.

5.2.9.2 Vital signs monitoring and record adverse events.

5.2.9.3 Check urinalysis for urinary tract infection if patient has symptoms suggestive of urinary tract infection.

5.2.9.4 Perform Uroflowmetry study for maximum flow rate, urodynamic study and PVR volume.

5.2.9.5 Collect 30 ml urine for analysis of the urinary NGF and cytokines levels.

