- (1) Local adverse event incidences (hematuria, micturition pain, UTI, urinary retention) will be reported by both treatment group and controlled group and by physiological systems as appropriate. Incidence of adverse events and the categories of adverse event severity between treatments will be analyzed. The coding system used will be COSTART.
- (2) The abnormalities of laboratory test results will be reported by patient list in the patients who have been tested for having severe adverse event.
- (3) The changes in physical examinations will be presented in the by-patient list.
- (4) All statistical tests used will be two-tailed with α = 0.05.

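### Non-visible hematuria in patients without symptoms is not systematically detected: every listed urinalysis depends on symptoms, and there is no routine baseline result

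*Protocol*

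**What the plan says.** Protocol section 2 opens its safety endpoints with "Local adverse event incidences (hematuria, miction pain, UTI, urinary retention", and the 3-month follow-up repeats the list. SAP 7.2 says "Local adverse event incidences (hematuria, micturition pain, UTI, urinary retention) will be reported by both treatment group and controlled group" and adds "Incidence of adverse events and the categories of adverse event severity between treatments will be analyzed". Neither document says whether hematuria means visible blood, microscopic blood or both.

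Urinalysis appears at three visits:

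- Screening (V0, item 5.2.1.6): "Urinalysis for WBC, RBC, pH, Protein, Glucose and Bacteria if patient has symptoms suggestive of urinary tract infection"
- Evaluation Visit I (V7, item 5.2.8.3): "Check urinalysis for urinary tract infection if patient has symptoms"
- Evaluation Visit II (V8, item 5.2.9.3): "Check urinalysis for urinary tract infection if patient has symptoms suggestive of urinary tract infection"

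Red cells are named only at V0. For V2 to V6, Protocol 5.2 lists "Vital signs monitoring, and confirm eligibility of patients" and the treatment itself (plus a diary handed out at V6), with no urinalysis. V1 lists none either.

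Urine is nevertheless obtained whatever the symptoms. The visit list has a 30 ml sample at V1, V7 and V8 for NGF and cytokines. Protocol 5.1 says a sample is taken at every visit, and its treatment procedure reads "Studied patients are requested to void completely before treatment. Urine samples (30 ml) will be collected".

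**The concern.** The trial directs shock waves at five bladder sites in six weekly sessions, and the protocol names hematuria first among the local events to watch for. Yet the only scheduled test that would show red cells is done on patients who complain, and at V7 and V8 its stated purpose is to find infection. The hematuria count will therefore hold blood that patients notice and report, plus whatever turns up in patients tested for symptoms.

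Two things are at stake. First, a count near zero could be read as showing that the bladder is not injured, when non-visible bleeding was never sought. Second, a patient with a positive test at V7 or V8 and no symptoms at V0 has no scheduled red-cell result to compare it with, so new blood cannot be told from old.

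**Working it through.** **The plan's own figures.** The documents give no number for hematuria. The only sample-size figure concerns PVR and reproduces: 24 per group, difference 50 mL, SD 60 mL and two-sided alpha 0.05 give 80.677% power by the noncentral t distribution on 46 degrees of freedom. Enrolment also reproduces: 48 / (1 − 0.20) = 60, or 30 per arm at 1:1. Neither figure bears on this point, and neither changes.

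**Visit by visit (Protocol 5.2).**

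| Visit | Timing | Urinalysis | 30 ml urine in visit list | Adverse-event recording in visit list |
|---|---|---|---|---|
| V0 | 2 weeks before treatment | Only with UTI symptoms; includes red cells | No | No |
| V1 | Session 1 | None | Yes | No (patient is told of possible events) |
| V2–V6 | Sessions 2–6 | None | No | No |
| V7 | 4 weeks after V6 | Only with symptoms; for UTI | Yes | Yes |
| V8 | 12 weeks after V6 | Only with UTI symptoms; for UTI | Yes | Yes |

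Three things follow.

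1. No visit has an unconditional test for blood.
2. No other scheduled test fills the gap. Exclusion criterion 4.3.7 implies a baseline urine culture, but a culture does not count red cells. Other laboratory tests in the safety section follow only a severe adverse event or an abnormal physical examination.
3. Testing the V7 and V8 samples alone would not be enough. They come 4 and 12 weeks after the last session and would miss short-lived bleeding. The informative urine is the void before each of sessions 2 to 6. The visit list collects none there, while 5.1 says urine is taken at every visit.

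**Effect on the between-arm comparison.** Let p1 and p0 be the true proportions with new hematuria on ESWT and placebo, and s the share of affected patients who are recorded, the same in both blinded arms. The recorded proportions are s·p1 and s·p0. Their ratio is unchanged; their difference is s·(p1 − p0), smaller by the factor s.

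**Illustration only; p1 and s are assumed.** The chance that none of 30 ESWT patients is recorded with hematuria is (1 − s·p1)^30.

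| Share recorded, s | p1 = 10%: expected cases; chance of none | p1 = 20%: expected cases; chance of none |
|---|---|---|
| 1 | 3.0; 4.2% | 6.0; 0.1% |
| 0.5 | 1.5; 21.5% | 3.0; 4.2% |
| 0.25 | 0.75; 46.8% | 1.5; 21.5% |
| 0.1 | 0.3; 74.0% | 0.6; 54.5% |

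For example, at p1 = 10% and s = 0.5: (1 − 0.05)^30 = 0.215. The table shows how an empty count can arise; it does not estimate how often it will.

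**The case against.** The strongest reply is that the endpoint may be meant as a clinically apparent event. Hematuria is listed beside pain on voiding, UTI and retention, and severity is graded by effect on daily activities. On that reading patient report is the intended method, and the definition in Protocol 6.1 (a new condition or a worsening of an existing one) already separates new from old visible bleeding. This is a fair reading, but the documents do not state it. Saying so would settle the definition; it would still leave non-visible bleeding unexamined in a trial that already has the urine.

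A reader might infer that hematuria without UTI symptoms goes undetected altogether. The documents do not support that. V7 and V8 record adverse events with no symptom condition, Protocol 6.1 requires all adverse events during the study to be documented, and 5.1 mentions adverse-event recording at the treatment visit even though the visit list omits it. The V7 wording refers to symptoms in general, which could include visible blood; only V0 and V8 restrict it to UTI symptoms.

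A reader might also infer that the comparison is biased between arms. Protocol 3.2 blinds both the patient and the observer, so under-recording should be similar in each. What stands is a loss of sensitivity.

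Practical objections also have weight. Patients on clean intermittent catheterization may enrol (4.2.15), so some incidental positives for blood are foreseeable. Asymptomatic bacteriuria is allowed (4.3.7), so leukocyte testing would add positives without serving this endpoint.

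**Conclusion.** The point holds as a gap in safety ascertainment. Non-visible hematuria in patients without symptoms is not systematically detected, and no routine baseline result separates new from pre-existing blood. Reported visible hematuria retains a recording route. The primary endpoint, sample size and alpha are unaffected.

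The size cannot be derived. It depends on the true hematuria rate and on the share that patients notice, and the documents give neither. For the same reason a stated loss of power would rest on invented rates; moreover, SAP 7.2 names Fisher's test only for the global response assessment and names no test for adverse events. The conclusion that sensitivity falls about equally in both arms assumes that blinding holds and that symptoms prompt testing at similar rates in each.

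The change should be made because it is cheap and because, without it, a low hematuria count cannot support a statement about bladder safety beyond visible or symptomatic bleeding.

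**What to change.** 1. **Protocol 5.2.** In every patient and both arms, test urine for blood by dipstick: the sample at V1 before the first session, the pre-session void at V2 to V6, and the samples at V7 and V8. Keep full urinalysis for patients with symptoms. Leukocyte testing is not needed for this purpose.
2. **Protocol 5.1 and 5.2.** Reconcile when urine is collected: 5.1 says every visit, the visit list says V1, V7 and V8.
3. **SAP 7.2.** Count hematuria as new or worse than the V1 result, and report visible and dipstick-only hematuria separately by arm.
4. **CRF.** Record dipstick result, visible blood and clean intermittent catheterization status at each of these visits, so that positives in patients who catheterize are flagged.

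**Cost.** Up to 8 dipsticks per patient (V1, five at V2 to V6, V7, V8), so at most 8 × 60 = 480 in the trial, and a few CRF fields. No extra visit, staff or invasive procedure is needed. The downside is some incidental positives to record.

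If the sponsor does not adopt the testing, SAP 7.2 should at least state that the endpoint covers only reported or symptomatic hematuria.
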